3 STUDY DESIGN

3.1 Description

This is an open label non-randomized pilot study to determine the clinical effects and safety of GCD-0449 in patients with hematologic malignancies who have undergone Allogeneic Hematopoietic Stem Cell Transplantation (HSCT) and have been diagnosed with chronic GVHD.

GDC-0449 will be given orally for a total of 6 months. In patients who are responsive to therapy with acceptable toxicity, the treatment period will be extended to 12 months. The initial dose will be given at 150 mg po daily. If Grade 2 hematologic or non-hematologic toxicities attributable to the study drug are observed, three different, consecutive dose reduction levels may be utilized:

- Level -1 (150 mg po every other day)
- Level -2 (150 mg po every three days)
- Level -3 (150 mg po twice a week)

All initial dose reductions will start at Level -1 and proceed to the next level if the toxicity in question persists. Dosing schedules will be dependent on what day of the week the patient starts the dose reduction level; for example, patients on Dose Level -1 with a Monday start would dose on Wednesday, Friday, Sunday, and so on.

3.2 Number of Patients

Twelve patients will be enrolled in this study. Sample size: 12 patients. Accrual rate: 1-2 patients monthly.

3.3 Number of Study Centers

This will be a single center study performed at the Huntsman Cancer Institute.

3.4 Study Duration

Estimated duration for the main protocol (e.g. from start of screening to last subject processed and finishing the study) is approximately two years. The accrual rate is estimated to be 1-2 patients per month. Patients will remain on study treatment for 6-12 months and will complete all study procedures in 12-18 months.

4 ELIGIBILITY CRITERIA

This eligibility checklist is used to determine patient eligibility and filed with signature in the patient research chart.

Patient No. _____

Patient's Initials: (L,F,M) _____

4.1 Inclusion Criteria

Yes/No (Response of "no" = patient ineligible)

4.1.1 _____ Age ≥ 18 years.

Because no dosing or adverse event data are currently available on the use of GDC-0449 in patients < 18 years of age, children are excluded from this study.

4.1.2 _____ ECOG performance status ≤ 2 (Karnofsky $\geq 60\%$, see [Appendix A](#)).

4.1.3 _____ Life expectancy of greater than 12 months

4.1.4 _____ Patients must have normal organ and marrow function as defined below:

- | | |
|--|--|
|  Leukocytes | $\geq 3,000/\text{mcL}$ |
|  Absolute neutrophil count | $\geq 1,500/\text{mcL}$ |
|  Platelets | $\geq 50,000/\text{mcL}$ |
|  Total Bilirubin | within normal institutional limits |
|  AST(SGOT)/ALT(SGPT) | $\leq 2.5 \times$ institutional upper limit of normal |
|  Creatinine | $\leq 1.5 \text{ mg/dl}$ |
| OR | |
|  Creatinine Clearance | $\geq 55 \text{ mL/min}$ using the Cockcroft-Gault equation for patients with creatinine |

levels above 1.5 mg/dl.

- 4.1.5** _____ Patients with chronic GVHD diagnosed within 3 years after hematopoietic stem cell transplant (HSCT) for any disease, with any graft, and any conditioning regimen with at least one manifestation secondary to fibrosis, including: sclerodermatous skin changes, dry mouth, dry eye, esophageal strictures, or vaginal GVHD
- 4.1.6** _____ Failure to respond to corticosteroids, defined as:
- Progression of chronic GVHD despite optimal first line therapy (> 0.5 mg/kg/day of prednisone dose equivalent (PDE) for two weeks) or;
 - No improvement after 4-8 weeks of sustained therapy. Sustained therapy should include 2 weeks of > 0.5 mg/kg/day of PDE or;
 - Inability to taper steroid dosage to less than 0.5 mg/kg/day of PDE without worsening of chronic GVHD or;
 - Need for second or third line therapy beyond corticosteroids and calcineurin inhibitors or sirolimus, irrespective of other criteria listed under the current section.
- 4.1.7** _____ The effects of GDC-0449 on the developing human fetus at the recommended therapeutic dose are unknown. For this reason and because Hh signal pathway inhibitors are known to cause interruption of the embryonic signaling pathway and may lead to serious or life-threatening birth defects, including brain deformities, facial malformation, heart problems, or abnormal organs. Therefore, women of child-bearing potential and men must use two forms of contraception (i.e., barrier contraception and one other method of contraception) at least 4 weeks prior to study entry, for the duration of study participation, and for at least 24 months post-treatment. For appropriate methods of contraception considered acceptable see [Appendix B](#). Should a woman become pregnant or suspect she is pregnant while participating in this study, she should inform her treating physician immediately.

Pregnancy Testing. Women of childbearing potential are required to have a negative serum pregnancy test (with a sensitivity of at least 25 mIU/mL) within 7 days prior to the first dose of GDC-0449 (serum or urine). A pregnancy test (serum or urine) will be administered every 4 weeks if their menstrual cycles are regular or every 2 weeks if their cycles are irregular while on study within the 24-hour period prior to the administration of GDC-0449. A positive urine test must be confirmed by a serum pregnancy test. Prior to dispensing GDC-0449, the investigator must confirm and document the patient's use of two contraceptive methods, dates of negative pregnancy test, and confirm the patient's understanding of GDC-0449 cause serious or life-threatening birth defects. Patients must continue highly effective contraception during therapy and for 24 months after the last dose of GDC-0449

Women of childbearing potential are defined as follows:

- Patients with regular menses
- Patients with amenorrhea, irregular cycles, or using a contraceptive method that precludes withdrawal bleeding
- Women who have had a tubal ligation

Women are considered not to be of childbearing potential for the following reasons:

- The patient has undergone hysterectomy and/or bilateral oophorectomy.
- The patient is post-menopausal defined by amenorrhea for at least 12 months in a woman > 45 years old.

Male patients should use condoms with spermicide, even after a vasectomy, during sexual intercourse with female partners while being treated with GDC-0449 and for 3 months after the last dose to avoid exposing an embryo or fetus to GDC-0449

4.1.8 _____ HIV-positive patients on combination antiretroviral therapy are eligible provided that they meet the following criteria in addition to the other protocol criteria:

- Cancer as the only AIDS-defining condition
- CD4 cell count ≥ 250 ,
- Treatment sensitive HIV and prospects for long term survival on the basis of HIV disease alone
- Willing to take anti-HIV therapy that will have minimal potential for pharmacokinetic interactions with GDC-0449.

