- All sexually active male subjects (including those who have undergone vasectomy) should utilize a barrier form of contraception **during study treatment and for 3 months after the last dose** as it is not known whether GDC-0449 that may be present in seminal fluid would cause serious or life-threatening birth defects in a fetus born to the female partner of a male subject. Males should also not donate sperm during treatment or up to 3 months after the last dose.
- All patients are prohibited from donating blood for 24 months after the last dose of GDC-0449.

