Note: GDC-0449 (Vismodegib) in combination with other agents could cause an exacerbation of any adverse event currently known to be caused by the other agent, or the combination may result in events never previously associated with either agent.

Additional Adverse Events

Serious or Life-threatening Birth Defect Effects of GDC-0449

Studies have demonstrated that inhibition of the Hh pathway in embryos results in brain, facial, and other midline defects, including holoprosencephaly or microencephaly, cyclopia, absent nose, cleft palate, tooth abnormalities, and bone development abnormalities (Bale, 2002). While the effects of GDC-0449 on the developing human fetus at the recommended therapeutic dose are unknown, women of childbearing potential and men must agree to use two methods of contraception (i.e., barrier contraception and another method of contraception) prior to study entry, for the duration of study participation, and for 24 months following treatment.

Women of childbearing potential are defined as follows:

- Patients with regular menses

- Patients with amenorrhea, irregular cycles, or using a contraceptive method that precludes withdrawal bleeding
- Women who have had a tubal ligation

Women are considered not to be of childbearing potential for the following reasons:

- The patient has undergone hysterectomy and/or bilateral oophorectomy.
- The patient is post-menopausal defined by amenorrhea for at least 12 months in a woman > 45 years old.

Women of childbearing potential are required to use two forms of acceptable contraception (refer to [Appendix B](#)), including one barrier method during participation in the study and for the 24 months following the last dose. All patients should receive contraceptive counseling either by the investigator or by an OB/gynecologist or other physician who is qualified in this area of expertise. If a woman of childbearing potential believes that her contraceptive method has failed, emergency contraception should be considered.

If a patient is suspected to be pregnant, GDC-0449 should be IMMEDIATELY discontinued and the study physician contacted. A positive urine test must be confirmed by a serum pregnancy test. If it is confirmed that the patient is not pregnant, the patient may resume dosing with GDC-0449.

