If a female patient becomes pregnant during therapy or within 24 months after the last dose of GDC-0449, or if the female partner of a male patient exposed to the drug becomes pregnant while the male patient is receiving GDC-0449 or within 3 months after the last dose of GDC-0449, the investigator must be notified in order to facilitate outcome follow-up.

Abortion, whether accidental, therapeutic, or spontaneous, should always be classified as serious. Any congenital anomaly/birth defect in a child conceived during the study or within 24 months after the last dose of GDC-0449 to a female patient or to a female partner of a male patient exposed to the agent during treatment or within 3 months after the last dose of GDC-0449 should be recorded and reported as an SAE.

In addition, it is not known whether GDC-0449 that may be present in seminal fluid would cause serious or life-threatening birth defects in a fetus born to the female partner of a male subject. Sexually active male subjects should utilize a barrier form of contraception, even those who have had a vasectomy, during study treatment and for 3 months after the last dose. Male patients should advise their partners to use an additional method of contraception during the study and for at least 3 months after discontinuation of GDC-0449. Male subjects should also not donate sperm during treatment or up to 12 months after the last dose.

Risk of Male Germ Cell Degeneration

[REDACTED]

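### The protocol gives men conflicting post-treatment contraception periods (24 or 3 months) and sperm-donation periods (3 or 12 months) and does not say which governs

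*Combined protocol and SAP*

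**What the plan says.** **Two methods, 24 months.** The main text of criterion 4.1.7 states that "women of child-bearing potential and men must use two forms of contraception", one of them a barrier, "for the duration of study participation, and for at least 24 months post-treatment". Section 14.3.1, under its additional adverse events text, says "women of childbearing potential and men must agree to use two methods of contraception", again with a barrier as one of the two, "for the duration of study participation, and for 24 months following treatment".

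**Condom or barrier, 3 months.** The last paragraph of 4.1.7 tells male patients to use condoms with spermicide, vasectomy or not, "while being treated with GDC-0449 and for 3 months after the last dose to avoid exposing an embryo or fetus to GDC-0449". Section 5.4.2 asks sexually active men for a barrier method over the same period. A later paragraph of 14.3.1 also sets a barrier for 3 months, and adds that men should advise their partners to use a further method for at least 3 months.

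**Sperm donation.** Section 5.4.2: "Males should also not donate sperm during treatment or up to 3 months after the last dose". Section 14.3.1: "Male subjects should also not donate sperm during treatment or up to 12 months after the last dose".

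**Reporting for partners of male patients.** Sections 5.4.2 and 14.3.1 use 3 months after the man's last dose for notifying a partner's pregnancy and for recording a birth defect as a serious event. Section 14.4.3 uses 12 months for the prenatal exposure form, and 24 months for following pregnancies to outcome and for expedited birth-defect reports.

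**The concern.** These are operative safety instructions. One set sits inside an eligibility criterion, and both 4.1.7 and 14.3.1 disagree with themselves. The protocol says that inhibitors of this pathway may lead to birth defects that are serious or threaten life, and that it is not known whether drug in seminal fluid carries this risk. With that uncertainty, men need one clear instruction. As written, what a man is told about the period after treatment depends on the section from which he is counselled. Whether a partner's pregnancy has to be reported likewise depends on the section that staff consult.

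**Working it through.** No sample size, power or event figure is involved, so the check sets every male-specific statement side by side.

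| Topic (men or their partners) | 4.1.7 main text | 4.1.7 last paragraph | 5.4.2 | 14.3.1 general sentence | 14.3.1 later paragraphs | 14.4.3 |
|---|---|---|---|---|---|---|
| Contraception period after treatment (months) | 24 | 3 | 3 | 24 | 3 | – |
| Methods named | two | condom with spermicide | barrier | two | barrier plus partner's method | – |
| Sperm-donation ban (months) | – | – | 3 | – | 12 | – |
| Partner-pregnancy notification (months) | – | – | 3 | – | 3 | – |
| Exposure form (months) | – | – | – | – | – | 12 |
| Pregnancy follow-up (months) | – | – | – | – | – | 24 |
| Birth-defect reporting, partner (months) | – | – | 3 | – | 3 | 24 |

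1. Contraception: 24 months in two places against 3 months in three. Gap: 24 − 3 = 21 months.
2. Sperm donation: 12 months in one place against 3 months in one. Gap: 12 − 3 = 9 months.
3. Number of methods: the two-method statements differ from the last paragraph of 4.1.7 and from 5.4.2, which each name only a condom or barrier. Condom plus spermicide does not count as two methods, because Appendix B lists a latex condom always used with spermicide as a single barrier form and lists secondary methods separately. The later paragraph of 14.3.1 does describe two methods per couple, so there the conflict is about duration.
4. Reporting, by example: a man's partner conceives 10 months after his last dose. Since 10 > 3, this is outside the notification window in 5.4.2 and 14.3.1. Since 10 < 12 and 10 < 24, it is inside the exposure-form and follow-up windows of 14.4.3. A birth defect in that child is outside the 3-month window of 5.4.2 and 14.3.1, on the natural reading of a long sentence, and inside the 24-month window of 14.4.3.
5. Contact with the site: sections 5.6 and 8.3 end scheduled follow-up 6 months after treatment. The longer periods run beyond it by 12 − 6 = 6 and 24 − 6 = 18 months, so there may be no later visit at which to correct an instruction.
6. People affected: the enrolment table in section 4.3 plans 5 + 1 = 6 men among 12 patients.

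The sentence closing the pregnancy-testing paragraph of 4.1.7 also gives 24 months. It is not counted because that paragraph concerns women of childbearing potential.

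**The case against.** **The statements can all be met at once.** A reader might infer that the rules are mutually exclusive. They are not. Each sets a minimum, and none of the shorter ones says that a man may stop other precautions or donate sperm once it ends. As a matter of logic, one course of conduct could satisfy every sentence. This stands. The defect is that the protocol does not say which minimum it requires.

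**The specific rule may override the general one.** The 24-month sentences cover women and men together. The 3-month sentences are written for men and, in 5.4.2 and 14.3.1, give a separate reason: drug in seminal fluid. The 3-month partner-notification window fits that reading. But the 24-month sentences name men expressly and name a barrier as one of the methods, and no order of precedence is stated. Nor can this reading explain the sperm-donation conflict, where two near-identical sentences, both specific to men, give 3 and 12 months.

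**Eligibility and consent.** A reader might infer that men would be screened or consented differently depending on the page. The documents do not support that for duration: a post-treatment period cannot be verified at screening, and the last paragraph of 4.1.7 sets no pre-entry rule. Only the number of methods could matter at entry. The consent pages are not available, so nothing can be said about what they contain.

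**Strength of the hazard.** It would go too far to say that male exposure is described as causing birth defects. Section 4.1.7 calls the effects on the human fetus unknown, and the seminal-fluid risk is stated as not known.

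**Scale.** This is a single-centre study with contraceptive counselling for all patients, which may limit variation in practice. It does not settle what the counselling should say.

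**Conclusion.** The point holds as an unresolved internal inconsistency in a patient-safety rule. Men are given 24 or 3 months of contraception (a 21-month gap) and a 3- or 12-month bar on sperm donation (a 9-month gap). The number of methods differs in some places, and partner-pregnancy and birth-defect windows of 3, 12 and 24 months do not line up. A man counselled from 5.4.2 alone would be given shorter periods than 4.1.7 or 14.3.1 state.

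The figure of 6 men is a planning target, not observed enrolment. Section 9.3 shows that the first 4 patients had already been assessed, which leaves at most 12 − 4 = 8 new patients, although earlier patients may still be within one of the longer periods. No endpoint, estimate or analysis is affected. The conclusion rests only on the current protocol text and assumes nothing about the consent form or actual practice.

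**What to change.** The sponsor must reconcile the main text and last paragraph of 4.1.7, section 5.4.2, and the general and male-specific paragraphs of 14.3.1. The result should be one duration and one number of methods for men, and one sperm-donation period. The windows for partner-pregnancy notification, the exposure form, pregnancy follow-up and birth-defect reporting in 5.4.2, 14.3.1 and 14.4.3 should then be aligned with that rule; otherwise those conflicts remain. The consent and counselling text should be checked against the reconciled wording. No duration or method is proposed here.

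The cost is a wording amendment with the IRB review that section 15.4 requires, plus a consent revision and a message to men already treated if the check shows that either is needed. Sample size, visits and analyses do not change.

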4.2 Exclusion Criteria

4.2.1 _____ Patients who have had chemotherapy or radiotherapy within 4 weeks (6 weeks for nitrosoureas or mitomycin C) prior to entering the study or those who have not recovered from adverse events due to agents administered more than 4 weeks earlier.

4.2.2 _____ Patients who are receiving any other investigational agents.

4.2.3 _____ Patients with known brain metastases should be excluded from this clinical trial because of their poor prognosis and because they often develop progressive neurologic dysfunction that would confound the evaluation of neurologic and other adverse events.

4.2.4 _____ History of allergic reactions attributed to compounds of similar chemical or biologic composition to GDC-0449

4.2.5 _____ Patients receiving any medications or substances that are strong inducers/inhibitors or substrates of CYP3A4/5, CYP2C9, CYP2C8, or CYP2C19 are ineligible. Because the lists of these agents are constantly changing, it is

important to regularly consult a frequently-updated list such as <http://medicine.iupui.edu/clinpharm/ddis/table.aspx>; medical reference texts such as the Physicians' Desk Reference may also provide this information. As part of the enrollment/informed consent procedures, the patient will be counseled on the risk of interactions with other agents, and what to do if new medications need to be prescribed or if the patient is considering a new over-the-counter medicine or herbal product.

- 4.2.6** _____ Patients with malabsorption syndrome or other condition that would interfere with intestinal absorption. Patients must be able to swallow capsules.
- 4.2.7** _____ Patients with clinically important history of liver disease, including viral or other hepatitis or cirrhosis are ineligible.
- 4.2.8** _____ Patients with uncontrolled hypocalcemia, hypomagnesemia, hyponatremia or hypokalemia defined as less than the lower limit of normal for the institution, despite adequate electrolyte supplementation are excluded from this study.
- 4.2.9** _____ Uncontrolled intercurrent illness including, but not limited to, ongoing or active infection, symptomatic congestive heart failure, unstable angina pectoris, cardiac arrhythmia, or psychiatric illness/social situations that would limit compliance with study requirements.
- 4.2.10** _____ Pregnant women are excluded from this study because GDC-0449 is a Hh pathway inhibiting agent with the potential for serious or life-threatening birth defects or abortifacient effects. Because there is an unknown but potential risk for adverse events in nursing infants secondary to treatment of the mother with GDC-0449, breastfeeding should be discontinued if the mother is treated with GDC-0449. These potential risks may also apply to other agents used in this study.
- 4.2.11** _____ More than 2 lines of therapy beyond corticosteroids with or without calcineurin inhibitors or sirolimus.
- 4.2.12** _____ Relapsed malignancy after transplantation

I certify that this patient meets all inclusion and exclusion criteria for enrollment onto this study.

Investigator Signature

Date

Time

4.3 Inclusion of Women and Minorities

Both men and women of all races and ethnic groups are eligible for this trial.

Racial Categories	Ethnic Categories				Total
	Not Hispanic or Latino		Hispanic or Latino		
	Female	Male	Female	Male	
American Indian/ Alaska Native	-	-	-	-	-
Asian	1	1	-	-	2
Native Hawaiian or Other Pacific Islander	-	-	-	-	-
Black or African American	1	1	-	-	2
White	3	3	1	1	8
More Than One Race	-	-	-	-	-
Total	5	5	1	1	12

5 TREATMENT PLAN

Treatment will be administered on an outpatient basis. Reported adverse events and potential risks are described in [Section 14](#). Appropriate dose modifications are described in [Section 6](#). No investigational or commercial agents or therapies other than those described below may be administered with the intent to treat the patient's malignancy.

5.1.1 Administration Schedule

- GDC-0449 is an oral drug. Patients should take GDC-0449 at approximately the same time according to their dose level, with or without food. Capsules should not be opened. If a patient misses a dose, he or she should be instructed not to take or make up that dose and to resume dosing with the next scheduled dose. Missed doses should not be made up. Patients will be instructed to bring all unused capsules and their medication diary (refer to [Appendix D](#)) to each study visit for assessment of compliance.
- Patients should be warned not to share their supply of GDC-0449.

- Investigators may dispense no more than a 32-day supply of GDC-0449.
- GDC-0449 will be given orally for a total of 6 months. In patients who are responsive to therapy with acceptable toxicity, the treatment period will be extended to 12 months. The initial dose will be given at 150 mg po daily. If Grade 2 hematologic or non-hematologic toxicities attributable to the study drug are observed, three different, consecutive dose reduction levels may be utilized:
 - Level -1 (150 mg po every other day)
 - Level -2 (150 mg po every three days)
 - Level -3 (150 mg po twice a week)

All initial dose reductions will start at Level -1 and proceed to the next level if the toxicity in question persists. Dosing schedules will be dependent on what day of the week the patient starts the dose reduction level; for example, patients on Dose Level -1 with a Monday start would dose on Wednesday, Friday, Sunday, and so on.

